#### Prior or concomitant medications

All medications will be coded using the World Health Organization-Drug Dictionary (WHO-DD) using the version currently in effect at Sanofi at the time of database lock.

- Prior medications are those the participant received prior to first IMP intake. Prior medications can be discontinued before first administration or can be ongoing during treatment period.
- Concomitant medications are any medications received by the participant concomitantly to the IMP during the DB treatment and OL periods.
- Post-treatment medications are those the participant received in the period running from the end of the concomitant medications period up to the end of the study.
- A given medication can be classified as a prior medication and/or as a concomitant medication and/or as post-treatment medication. If it cannot be determined whether a given medication was taken prior or concomitantly or post, it will be considered as prior, concomitant, and post-treatment medication.

Any prior MS disease modifying therapy use will be summarized by the standardized medication name in the randomized population, sorted by decreasing frequency in the Overall group. Additionally, prior, concomitant, and post-treatment medications will be summarized for the randomized and exposed population, by anatomic and therapeutic level. The summaries will be

sorted by decreasing frequency of anatomic category (ATC) based on incidence in the tolebrutinib group. In case of equal frequency, alphabetical order will be used. Participants will be counted once in each ATC category (anatomic or therapeutic) linked to the medication.

#### 5.4 APPENDIX 4 DATA HANDLING CONVENTIONS

#### Analysis windows for time points

The following analysis windows will decide how the scheduled and/or unscheduled visits will be used in the by-visit analyses of efficacy, safety, and PD variables.

A measurement (scheduled or unscheduled) will be used if it is available and measurement date is within the analysis window.

After applying these time windows, if multiple assessments are associated to the same time point, the closest from the targeted study day will be used. If the difference is a tie, the value after the targeted study day will be used. If multiple valid values exist within a same day, then the first value of the day will be selected.

If there is no measurement for a given parameter in an analysis window, data will be considered missing for the corresponding visit and similar quarterly windows will be applied if the treatment period extends beyond 48 months.

AVISIT	Target Day	EDSS		MRI		T25FW, SDMT, (	9-HPT, CVLT-II	MSQol EQ-5D	54, -5L
	-	Start Day	End Day	Start Day	End Day	Start Day	End Day	Start Day	End Day
Baseline	1	-40	1	-40	1	-40	1	-40	1
Month 3	84	2	126			2	126		
Month 6	168	127	210	2	252	127	210	2	252
Month 9	252	211	294			211	294		
Month 12	336	295	378	253	420	295	378	253	420
Month 15	420	379	462			379	462		
Month 18	504	463	546	421	588	463	546	421	588
Month 21	588	547	630			547	630		
Month 24	672	631	714	589	840	631	714	589	756
Month 27	756	715	798			715	798		
Month 30	840	799	882			799	882	757	924
Month 33	924	883	966			883	966		
Month 36	1008	967	1050	841	1176	967	1050	925	1092
Month 39	1092	1051	1134			1051	1134		
Month 42	1176	1135	1218			1135	1218	1093	1260
Month 45	1260	1219	1302			1219	1302		
Month 48	1344	1303	1386	1177	1512	1303	1386	1261	1428
		Start Day	/: last visit	window upp	per limit +1				
		End Day: EOS visit date							
EOS		Nominal	visit (9000	)					
FU for participants				≥Dat	e of EOS+	1			
not entering LTS				Nomin	al visit (807	10)			
		Start Day	/: date of d	iscontinuati	ion+1 Idulad vieit	window			
		End Day	start of th	e next sche	ioit	WINDOW			
FU for participants not entering LTS pEOT		≥Date of EOS+1 Nominal visit (8010) Start Day: date of discontinuation+1 End Day: start of the next scheduled visit window Map to the closest scheduled visit							

#### Table 7 - Analyses window definition of efficacy variables

	Target	Hemate bioche except	ology, mistry liver	Vital Signs C-SS B-HC	s, RS, :G								
AVISIT	Day	tests		Test Weid		Weigh	nt	ECG		Urina	lysis	Coagu	lation
		Start	End	Start	End	Start	End	Start	End	Start	End	Start	End
		Day	Day	Day	Day	Day	Day	Day	Day	Day	Day	Day	Day
Screening	-1	-40	-1	-40	-1	-40	-1	-40	-1	-40	-1	-40	-1
Day 1	1	1	1	1	1	1	1						
Month 1	28	2	42										
Month 2	56	43	70										
Month 3	84	71	98	2	126	2	126	1	126	1	210		
Month 4	112	99	126										
Month 5	140	127	154										
Month 6	168	155	210	127	210	127	252	127	210				
Month 9	252	211	294	211	294			211	294				
Month 12	336	295	378	295	378	253	420	295	504	211	420		
Month 15	420	379	462	379	462								
Month 18	504	463	546	463	546	421	588			421	588		
Month 21	588	547	630	547	630								
Month 24	672	631	714	631	714	589	756	505	840	589	756		
Month 27	756	715	798	715	798								
Month 30	840	799	882	799	882	757	924			757	924		
Month 33	924	883	966	883	966								
Month 36	1008	967	1050	967	1050	925	1092	841	1176	925	1092		
Month 39	1092	1051	1134	1051	1134								
Month 42	1176	1135	1218	1135	1218	1093	1260			1093	1260		
Month 45	1260	1219	1302	1219	1302								
Month 48	1344	1303	1386	1303	1386	1261	1386	1177	1386	1261	1386		
EOS		Start Day Nominal	/: last visi visit (900	it windov 0)	v upper	limit +1; E	End Day	EOS vis	sit date				
Liver Function test		Nominal	visit at M	onth 0.5	, 1.25, 1	.5, 1.75, 1	2.25, 2.5	5, 2.75, 7	, 8, 10, 1	1.			
FU for			>:	=Date of	EOS+1								
participants			No	minal vis	sit (8010	)							
who do													
not enter													
		Start Day window	/: date of	disconti	nuation+	-1; End D	ay: start	of the ne	ext sche	duled visi	it		
pEOT		Map to th	ne closes	t schedu	led visit								

#### Table 8 - Analysis window definition of safety variables

Note: Analysis windows in open-label period can follow the same rule except that the first open-label dose date is Day 1 in that period

	Taurat	Plasm samp (NfL), serum	na les n	0		Lymphoc	yte	Diacede		
AVISIT	Target Day	samp (Chi3l	les L1)	(lq levels)	mpies	flow cyto	flow cvtometrv		archiving	
		Start Day	Énd Day	Start Day	End Day	Start Day	End Day	Start Day	End Day	
Screening	-1							-40	-1	
Day 1	1	1	1	1	1	1	1			
Month 1	28									
Month 2	56									
Month 3	84	2	126							
Month 4	112									
Month 5	140									
Month 6	168	127	252	2	252					
Month 9	252									
Month 12	336	253	504	253	504					
Month 15	420									
Month 18	504									
Month 21	588									
Month 24	672	505	840	505	840					
Month 27	756									
Month 30	840									
Month 33	924									
Month 36	1008	841	1176	841	1176					
Month 39	1092									
Month 42	1176									
Month 45	1260									
Month 48	1344	1177	1386	1177	1386					
		Start Day: last visit window upper limit + 1; End Day: EOS visit date								
EOS		Nomina	ıl visit (9	000)						
		Start Da	ay: date	of discontinuat	ion + 1;					
		End Day: start of the next scheduled visit window								
pEOT		Map to the closest scheduled visit								

#### Table 9 - Analysis window definition of PD variables

#### **Unscheduled visits**

Unscheduled visit measurements of laboratory data, vital signs, and ECG will be used for computation of baseline, the last on-treatment value, analysis according to PCSAs, and the shift summaries for safety. They will also be included in the by-visit summaries (central lab only for laboratory data and ECG) if they are re-allocated to scheduled visits based on the analysis windows defined above.

#### 5.5 APPENDIX 5 ANALYSES SUPPORTING THE INTEGRATED SUMMARY OF SAFETY

Below are the additional analyses supporting the integrated summary of safety.

- Time to study intervention discontinuation for any reason (except switch to OL due to 6M-CDP) and due to AE using the KM method
- Exposure to study intervention by duration in participant years (≥24, ≥48, ≥72, ≥96, ≥120, ≥144, ≥168 weeks)
- Exposure to study intervention by subgroups in participant years
  - Age at screening (>40,  $\leq$ 40 years)
  - Sex (Male or Female)
  - Age by sex (>40 & male, >40 & female,  $\leq$ 40 & male,  $\leq$ 40 & female)
  - Race (White, Black or African American, Asian, Other)
  - Weight in kg ( $<70, \ge 70$  to  $<90, \ge 90$ )
  - BMI in kg/m^2 (<25,  $\geq 25$  to <30,  $\geq 30$ )
  - Baseline EDSS ( $<4, \geq 4$ )
  - Geographic region (US, non-US; Eastern Europe, Western Europe, North America, rest of the world [ROW])
  - Prior disease modifying therapy use (yes, no)
- Most frequent TEAEs sorted by relative risk and the corresponding forest plot
- Most frequent TEAEs sorted by risk difference and the corresponding forest plot
- Summary of TEAEs by primary SOC
- Summary of TEAEs by primary SOC, HLT and PT
- TEAEs leading to permanent study intervention discontinuation by exposure intervals (based on 24-week intervals)
- Incidence rate of post-treatment SAEs related to IMP
- Summary of TE AESIs by category, primary SOC and PT
- Summary of other TEAE groupings of interest by category, primary SOC and PT
- Incidence rate and relative risk ratio for TE AESIs and other selected AE groupings (COVID-19, suicidal behavior, malignancy) and the corresponding forest plot
- Incidence rate and risk difference for TE AESIs and other selected AE groupings (COVID-19, suicidal behavior, malignancy) and the corresponding forest plot
- Detailed summary for each AESI and other AE groupings
- Summaries of PTs occurring in at least 2/3/5% of participants on tolebrutinib and with a greater incidence compared to placebo by primary SOC and PT

- Boxplots and shift plots of the maximum values of ALT, AST, ALP and total bilirubin during treatment
- Incidence rates of TEAEs, TE SAEs, TEAEs leading to permanent study intervention discontinuation and AESIs/other AE group events by subgroups with corresponding forest plots

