6.6.1 Open-label treatment

If a participant achieves the primary endpoint (6-month CDP), they may, in conjunction with the Treating Investigator, choose to receive one of the following:

- 1. To switch to open-label SAR442168 treatment; OR
- 2. To switch to a non-study treatment approved for NRSPMS in their respective country. In this case, the participant will permanently discontinue the IMP and will be encouraged to remain in the study for planned clinical visits (see Section 7.1.1) until common study end.

In case the participant switches to open-label SAR442168 treatment, he/she will need to be monitored for liver function tests after the first open-label dose at Weeks 2, 3, 4, 5, 6, 7, 8, 9, 10, 11, and 12, and then monthly for the next 9 months. After that, the schedule visits timepoints per SoA will be resumed (ie, every 3 months), until the common study end. Whenever a timepoint will coincide with a scheduled visit as per SoA (Section 1.3), the full scheduled visit assessments will be performed instead of the liver monitoring testing alone.

For participants achieving 6-month CDP, the Investigator must ensure that the participant does not meet any of the following criteria prior to the switch to open-label SAR442168 treatment:

• Current alcohol intake >2 drinks per day for men and >1 drink per day for women (1 drink = approximately 14 grams of alcohol = 350 mL beer = 140 mL wine = 40 mL of spirits).

- Acute liver disease, cirrhosis, chronic liver disease (unless considered stable for >6 months).
- Confirmed ALT >1.5 × ULN OR AST >1.5 × ULN OR ALP >2 × ULN (unless caused by non-liver-related disorder or explained by a stable chronic liver disorder) OR total bilirubin >1.5 × ULN (unless due to Gilbert syndrome or non-liver-related disorder).

Liver function tests will be performed for all participants prior to the start of open-label treatment.

Should the participant and Investigator opt for the provision of open-label medicine, they will remain blinded to the original treatment assignment.

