9.2 SAMPLE SIZE DETERMINATION

Approximately 1700 participants will be screened to achieve up to 1290 randomly assigned to study intervention (2:1 randomization ratio of SAR442168 to placebo). This study is planned as an event-driven trial based on 6-month CDP. The study will continue until approximately 288 events are projected to have occurred to provide 80% power to detect a 30% risk reduction in 6-month CDP with SAR442168 compared to placebo (2-sided α =0.05). The following assumptions were used for the calculations: 2-year placebo event rate of 23.6%; annual discontinuation rate of 10%; constant hazard rates using a log-rank test; estimated enrollment period of 24 months with last randomized participant followed for 24 months.

Actual recruitment and disability event rates may vary; therefore, it is possible to stop with a reduced sample size of around 1100 and still maintain study power by extending the duration of the trial, if needed, to reach approximately the same number of events. For example, it could be that the last randomized participant is followed for around 30 months instead of 24, if necessary. Additional recruitment of participants will not substantially reduce the trial duration. In any case, the power is based on the number of events, and the actual trial duration will be dependent on the observed placebo rate and treatment effect.

Note: "Enrolled" means a participant's, or their legally acceptable representative's, agreement to participate in a clinical study following completion of the informed consent process. Potential participants who are screened for the purpose of determining eligibility for the study, but do not participate in the study, are not considered enrolled, unless otherwise specified by the protocol.

Amended Clinical Trial Protocol 12 SAR442168-EFC16645 - tolebrutinib 20-Dec-2023 Version number: 1

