#### 3.2.2 Main analytical approach

The primary analysis of the primary endpoint, time to onset of 6-month CDP, will be performed on the ITT population. The null hypothesis is no treatment difference between tolebrutinib and placebo, and the alternative hypothesis is that there is a between-treatment difference. The study will be declared positive if the null hypothesis for the primary endpoint of 6-month CDP for tolebrutinib compared to placebo is rejected at the 2-sided 0.05 significance level.

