## 4 SAMPLE SIZE DETERMINATION

Approximately 1700 participants will be screened to achieve up to 1290 randomly assigned to study intervention (2:1 randomization ratio of tolebrutinib to placebo). This study is planned as an event-driven trial based on 6-month CDP. The study will continue until approximately 288 events are projected to have occurred to provide 80% power to detect a 30% risk reduction in 6-month CDP with tolebrutinib compared to placebo (2-sided  $\alpha = 0.05$ ). The following assumptions were used for the calculations: 2-year placebo event rate of 23.6%; annual discontinuation rate of 10%; constant hazard rates using a log-rank test; estimated enrollment period of 24 months with the last randomized participant followed for 24 months.

Actual recruitment and disability event rates may vary; therefore, it is possible to stop with a reduced sample size of around 1100 and still maintain study power by extending the duration of the trial, if needed, to reach approximately the same number of events. For example, it could be that the last randomized participant is followed for around 30 months instead of 24, if necessary. Additional recruitment of participants will not substantially reduce the trial duration. In any case, the power is based on the number of events, and the actual trial duration will be dependent on the observed placebo rate and treatment effect.

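### The Kaplan-Meier curve for stopping study intervention because of an adverse event has no competing-event rule, so read as a risk it runs above the share of participants who actually stop for that reason

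*SAP*

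**What the plan says.** SAP 5.5 (Appendix 5) plans "Time to study intervention discontinuation for any reason (except switch to OL due to 6M-CDP) and due to AE using the KM method". The bullet does not say what is censored, which treatment period is covered, or whether the curve is meant as a risk in the trial population or as a net risk while on treatment.

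The open-label route is in Protocol 6.6.1: a participant who reaches 6-month CDP may choose "To switch to open-label SAR442168 treatment; OR" move to a non-study therapy, or may stay on double-blind treatment. Three other places bear on what happens next:

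- Protocol 7.1.1 counts open-label use among the reasons for discontinuing treatment. It also bars anyone who stops permanently for a reason other than 6-month CDP from open-label drug.
- SAP 3.1 closes the double-blind treatment-emergent period at the first open-label dose.
- SAP 1.1 and SAP 5.2 use the term study intervention for double-blind and open-label treatment together.

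The only rates available are the sample size assumptions in Protocol 9.2 and SAP 4: "2-year placebo event rate of 23.6%; annual discontinuation rate of 10" per cent, with a 30% risk reduction.

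**The concern.** Kaplan-Meier knows two states, event and censored. For the AE curve, a participant who stops for another reason or dies must therefore be censored, and so must one who switches to open label if the curve covers double-blind treatment. None of these participants can later have the event. Censoring them makes 1-KM estimate the risk in a hypothetical setting where nobody leaves treatment for any other cause. That is at or above the real proportion stopping for an AE, whatever the rates.

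The any-reason curve has a related gap. It states that the open-label switch is not an event, but not how a switcher is handled from then on.

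At stake is a tolerability figure in the safety summary that a reader will naturally take as the percentage of participants who stop for an AE by a given time.

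**Working it through.** **Check on the design inputs.** SAP 4 says "approximately 288 events are projected to have occurred to provide 80% power to detect a 30% risk reduction in 6-month CDP", with a "2:1 randomization ratio of tolebrutinib to placebo"; SAP 3.2.2 tests at the two-sided 0.05 level. By the Schoenfeld formula, power = Φ(√(288 × 2/3 × 1/3) × |ln 0.70| − 1.96) = Φ(8 × 0.3567 − 1.96) = Φ(0.893) = 81.4%, against 80% stated. In the SAP's reduced-size example of about 1100 participants, "the last randomized participant is followed for around 30 months instead of 24". Exponential hazards, uniform 24-month accrual and 10% annual dropout then give 289 expected events, close to 288. The hazards below are therefore consistent with the plan.

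**Inputs from the documents**
- Placebo CDP hazard: −ln(1 − 0.236)/2 = 0.1346 per year.
- Tolebrutinib CDP hazard: 0.70 × 0.1346 = 0.0942 per year.
- Total discontinuation hazard: D = −ln(0.90) = 0.1054 per year.

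**Inputs assumed, because the documents give none**
- AE hazard h of 0.01 to 0.05 per year, constant and equal in both arms. Other-reason stops (death included) are the remainder, D − h.
- A fraction u of participants reaching CDP switches, with u from 0 to 1. The switch hazard is u times the CDP hazard and starts at 0.5 years, since 6-month confirmation is needed first.
- The 10% is taken as treatment discontinuation. Protocol 9.2 does not say whether it means treatment or study discontinuation.

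**Formulas at 3 years**, with b = D + u × CDP hazard:
- 1-KM = 1 − exp(−3h)
- Cumulative incidence = (h/D)(1 − e^(−0.5D)) + (h e^(−0.5D)/b)(1 − e^(−2.5b))

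**Worked case: placebo, h = 0.03, u = 1.** Here b = 0.1054 + 0.1346 = 0.2400. The first term is 0.2847 × 0.0513 = 0.0146. The second is (0.03 × 0.9487/0.2400) × 0.4511 = 0.0535. Cumulative incidence is 6.8%; 1-KM is 1 − e^(−0.09) = 8.6%; the excess is 1.8 points.

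| AE hazard per year | 1-KM at 3 years | Excess, u = 0 (both arms) | Excess, u = 0.5 (placebo / tolebrutinib) | Excess, u = 1 (placebo / tolebrutinib) |
|---|---|---|---|---|
| 0.01 | 3.0% | 0.4 | 0.5 / 0.5 | 0.7 / 0.6 |
| 0.02 | 5.8% | 0.7 | 1.0 / 0.9 | 1.3 / 1.1 |
| 0.03 | 8.6% | 0.9 | 1.4 / 1.2 | 1.8 / 1.5 |
| 0.05 | 13.9% | 1.1 | 1.9 / 1.6 | 2.6 / 2.2 |

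The u = 0 column also shows roughly what remains if the curve runs through open-label treatment, where a switch ends nothing.

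**Any-reason curve, double-blind reading, placebo.** 1-KM = 1 − 0.9³ = 27.1%. With the switch as a competing event, the cumulative incidence is 25.4% (u = 0.5) to 23.9% (u = 1).

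**Early AE stops.** Suppose all AE stops (3-5% in total) fall in the first 0.25 years. No switch has happened yet, and only other-reason stops compete. For 3%, h = −ln(0.97)/0.25 = 0.1218. With other-reason hazard 0.1054, cumulative incidence = (0.1218/0.2272)(1 − e^(−0.0568)) = 2.96%, an excess of 0.04 points. For 5% it is 0.06.

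**Between arms.** At AE hazards of 0.03-0.05 and u of 0.5-1, the placebo excess exceeds the tolebrutinib excess by 0.14 to 0.42 points. With 430 and 860 participants and follow-up spread over 24 to 48 months, the standard error of the arm difference is about 2.0 to 2.5 points. The distortion is thus about 0.1 to 0.2 standard errors.

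**The case against.** The strongest reply is that Kaplan-Meier answers a legitimate question: the net risk of an AE stop while on treatment, under independent censoring. The exception in the any-reason curve also looks deliberate, since moving to active drug after an efficacy event is not a failure to tolerate treatment. This stands as a matter of estimand, but the SAP does not say that a net risk is meant.

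Second, the term study intervention can include open label (SAP 1.1, 5.2). On that reading a switch need not end observation. This also stands, and it is why the switch counts only on the double-blind reading. Other-reason stops and death compete on either reading.

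Third, a reader might infer that the 3-year risk will be overstated by a definite amount of one to a few points. The documents do not support that. The AE rate, reason split and uptake are all assumed, switching is optional and needs liver checks first (Protocol 6.6.1), and the liver injury cases in Protocol 2.3 arose in Months 1 to 3, where the excess nearly vanishes. Other assumptions also go higher: with 10% per year for other reasons alone, AE 5% per year and full uptake after 24 weeks, the placebo excess is 3.4 points.

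Fourth, a reader might infer a material bias between the arms, or a fault in any mismatch with the disposition table. The first is about 0.1 to 0.2 standard errors. The second is not a defect: with variable follow-up, no 3-year curve of either kind equals a crude percentage.

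Finally, SAP 3.6.2 and 5.2 already plan crude counts of AE discontinuations and disposition by reason, and SAP 5.5 adds counts by 24-week interval. The curve is therefore not the only source.

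**Conclusion.** The point holds as a minor one. The direction is certain: with competing events censored, 1-KM cannot lie below the cumulative incidence. The size is conditional. Under constant AE rates of 1-5% per year, a 10% annual total and 0-100% switch uptake after 0.5 years, the 3-year excess is about 0.4 to 2.6 points; it is near zero if AE stops cluster in Months 1 to 3. The upper part of the range needs the double-blind reading and full uptake. The curve is one descriptive safety display: SAP 3.6 plans no safety testing, and the primary and secondary efficacy analyses are unaffected.

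**What to change.** In SAP 5.5:

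- State whether the curves cover double-blind treatment only or double-blind plus open label.
- For discontinuation due to AE, report the Aalen-Johansen cumulative incidence, with other-reason discontinuation, death and (on the double-blind reading) open-label switch as competing events. Reaching the common study end on treatment remains ordinary censoring.
- For any-reason discontinuation on the double-blind reading, treat the open-label switch as a competing event.
- If a net risk on treatment is also wanted, keep the Kaplan-Meier curve and label it as such.

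The cost is a sentence or two of SAP text and a standard procedure option. Stop reasons and open-label switches are already needed for the disposition summary in SAP 5.2, so no new data are required. The downside is a slightly lower displayed risk and one changed or added curve.
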